The proposed study tests the novel DilaCheck® device *in vivo*. The target population is women presenting to the hospital for evaluation of labor or admitted to the Labor and Delivery unit for management of the first stage of labor. The Sponsor (Elm Tree Medical Inc.) trains providers working on the Labor and Delivery unit in the use of DilaCheck®. After informed consent, each patient participant is randomized to receive either two cervical dilation examinations with standard methods or two cervical dilation examinations using the device. Two practitioners complete the cervical examinations separately. The primary outcome is inter-examiner agreement between the control and device arms. Secondary outcomes include agreement of subjective measurements with DilaCheck® measurements over time, agreement of providers' device readings with a blinded reviewer's, patient and provider satisfaction, and documentation of adverse events. Planned enrollment is 50 participants over one year. We hypothesize that the device will increase agreement between the two practitioners from about 49% to 90%, as demonstrated in the simulator trial. The long-term objective is to validate DilaCheck® for use in increasing precision in cervical dilation measurements so that this tool may be available to Labor and Delivery providers to enhance quality of care for pregnant mothers. Increased precision in cervical dilation measurements will enable providers

to make better recommendations for admission to the hospital, augmentation or induction of labor, and cesarean section.

The proposed study is a randomized, controlled trial comparing inter-examiner agreement of standard methods for measuring cervical dilation to a novel medical device. The research population is pregnant women in the first stage of labor.

TRIAL PROTOCOL

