Trial Coordination. After training, the Sponsor or the trial coordinator will orient the provider to the study protocol and assign every provider a unique Provider Number. The trial coordinator will arrange with the hospital staff to conduct the trial at scheduled times during the study period. Administration of the trial requires two hospital providers who have been trained to use the device, the trial coordinator,

and a patient.

Patient Enrollment. Hospital providers will screen patients who have been admitted to the Labor and Delivery unit for eligibility. Posters advertising the trial will also be displayed on the Labor and Delivery unit. Once identified, hospital providers will ask eligible patients if they are interested in participating. If a patient indicates interest, the trial coordinator will complete an informed consent. The patient will sign the Patient Informed Consent Form.

Randomization. The trial coordinator will assign the participant a Subject Number from one to 50, in sequential order. (The first patient enrolled is assigned #1, the second enrolled is assigned #2, and so on.) The trial coordinator will then randomize the patient to either the Control Group or the Device Group using a randomization matrix generated by a computer randomization program.

Data Collection. The trial coordinator will inform two trained providers that the patient has agreed to participate in the trial. The trial coordinator will accompany one hospital provider to the patient's hospital room. The second provider will wait outside the room, in a place where s/he cannot hear the interaction in the room. The trial coordinator will re-affirm consent with the patient.

If the patient is randomized to the Control Group: The first provider will introduce him/herself and inform the patient that s/he is going to conduct a cervical examination. The trial coordinator will record the time of the first exam. The provider will complete a cervical examination following the standard techniques s/he uses on a regular basis, using sterile gloves. The provider will dispose of the gloves. The first provider will write his/her measurement of cervical dilation on the first Data Collection Form and fold the sheet of paper. Readings may be integers or fractional answers. The coordinator will take the folded sheet of paper and will not read the value. The first provider will then leave the hospital room. S/he will not speak to the second provider.

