With regard to missing data, if a patient is missing one or both of the cervical dilation readings, she will be excluded from analysis of the primary outcome. However, if she has filled out a survey, this data will be used in the analysis of secondary outcomes since it may include important data accounting for why the patient was unable to have both examinations. If a patient or provider is missing one or more answers to a survey question, then the response to that question will be omitted from the analysis. The statistical analysis will not include imputing missing data.

The Sponsor will provide the trial coordinator, principle investigator, and other

involved TJU staff access to the statistical analysis and article draft and provide them with time to provide feedback and insight into all statistical analyses.

Study Device Specifications. There are no hazardous materials involved in this trial. The study device is made of soft, medical grade, biocompatible components. The device is sterilized using gamma radiation. The device is not anticipated to present any risk above that of a standard cervical dilation examination with a sterile glove. It is tested for reliability, and all components have multiple attachment points so that if one attachment point fails, it will still be attached to another component or the provider's hand and thus will not be left in the patient.

Bias. Unfortunately, it is not feasible to blind patients and providers to group assignment. However, keeping the second provider blinded to the first provider's measurement will decrease bias. Randomization using a computer generation program will also eliminate assignment bias.

Potential Problems. Given the acuity of Labor and Delivery, one anticipated challenge is enrollment. Women in labor may be hesitant to participate in any clinical trial or to participate in the validation of a novel device. We will offer a small incentive for participation via a modest gift certificate of a size not large enough to coerce patients into participating. The trial coordinator will answer any questions the patient has regarding the trial and respond to any concerns that arise in an open, patient, and honest manner.

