Potential Risks of Study Participation. The device is not anticipated to present any risk above that of a standard cervical dilation examination with a sterile glove. Potential risks to the patient include loss of confidentiality, discomfort with cervical examinations, a theoretical increased risk of infection, rupture of membranes, and inconvenience. For the provider, there is not anticipated to be any risk above that of performing a standard cervical dilation examination with a sterile glove.

Recruitment and Informed Consent. The sampling plan will ensure that all eligible patients are offered the opportunity to participate, regardless of race, ethnicity, or

socioeconomic status. The trial coordinator will consent patients in a private room or area. Consent will be documented with signatures of the trial coordinator and the patient on the Patient Informed Consent Form. Patients will receive a copy of the Patient Consent Form.

Randomization. Patients will be randomized to a treatment group using a computer-generated randomization program to eliminate assignment bias.

Confidentiality. Only the trial coordinator, the Sponsor, and the PI will have access to individually identifiable private information about human subjects. The hospital providers will likely have access to this information through the hospital medical record, but they will not be provided with the data through participation in the trial. The trial coordinator will store trial materials in a locked space at TJU. All physical materials obtained by Elm Tree Medical will be stored in a locked file at the Elm Tree Medical Inc. office. The trial coordinator will provide Elm Tree Medical with an electronic report of data collected. Any data entered into electronic form on TJU or Elm Tree Medical computers will be password-protected.

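### No allocation concealment is described, so the next arm could be known before consent is completed; computer generation alone does not support the claim that assignment bias is eliminated

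*Combined protocol and SAP*

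**What the plan says.** All references are to the combined protocol and SAP.

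- **First approach (Patient Enrollment).** Hospital providers screen admitted patients, and "hospital providers will ask eligible patients if they are interested in participating".
- **Consent (Patient Enrollment).** "If a patient indicates interest, the trial coordinator will complete an informed consent".
- **Numbering (Randomization, Trial Protocol).** "The trial coordinator will assign the participant a Subject Number from one to 50, in sequential order".
- **Allocation (same paragraph).** The coordinator is then to "randomize the patient to either the Control Group or the Device Group using a randomization matrix generated by a computer randomization program".
- **Order of events (Protocol Summary).** "After informed consent, each patient participant is randomized" to one of the two arms.
- **Claim about bias (Bias).** "Randomization using a computer generation program will also eliminate assignment bias".
- **The claim repeated (Randomization, Protection of Human Subjects).** "Patients will be randomized to a treatment group using a computer-generated randomization program to eliminate assignment bias".

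The Trial Coordination paragraph also has the coordinator schedule sessions with hospital staff. The Bias paragraph says that patients and providers cannot be blinded. The coordinator attends the examinations in both arms and photographs the device readings, and so knows every past allocation.

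**The concern.** Random generation and concealment are separate safeguards. Generation ensures that the sequence owes nothing to anyone's preference. Concealment ensures that the people entering patients cannot act on the next term of that sequence. The protocol describes the first and credits it with the effect of both.

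The gap matters here because the women are mixed. Eligibility covers women admitted for induction who are not yet in labor and women in first-stage labor with a working epidural. How easily two examiners agree may plausibly depend on the state of the cervix. If knowledge of the next arm influenced when a session was held or a consent completed, the arms could differ in how measurable the women are, and the primary comparison of agreement would carry that difference. The listed patient data include epidural status but not whether the woman was being induced or was already in labor, so an imbalance would be only partly visible afterwards.

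This point concerns which women enter which arm. The choice of examiners after allocation is a separate matter.

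**Working it through.** **1. Is the next arm knowable under the text as written?** Subject Numbers run in order, so the next number is always known. The arm comes from a generated matrix used by the person who completes consent. No section mentions envelopes, a central or electronic release, an independent holder of the list, blocking, or any bar on viewing upcoming rows. Consent before randomization does not settle the matter: if the row for the next number can be seen, the arm is known while consent is being sought.

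**2. What concealment would change.** A visible list reveals all 50 assignments. Suppose instead that the list is concealed and holds exactly 25 per arm in random order (an assumption; the protocol plans 25 per group but states no blocking). The best guess from past assignments is then right on average

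25 + (4^25 / C(50,25) − 1)/2 = 25 + (8.907 − 1)/2 = 28.95 times in 50, against 25 by chance.

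**3. The plan's own figures.** The Power Calculation projects 49% agreement under control and 90% with the device, a contrast of 90 − 49 = 41 points. With its standard deviation of 23, two-sided alpha of 0.05 and 80% power, the normal formula gives 2 × (23 × (1.960 + 0.842)/41)² = 4.94, so five per arm, as stated if five is read as per arm. Nothing below depends on that sample size; only the 41-point contrast and the 90% are used.

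**4. Possible size of the bias.** Every input here except the 90% and the 41 is an assumption.

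- Half of the women are easy to measure and half are hard.
- A share f of entries is steered, easy cases to the device and hard cases to control. Steering in mixed directions would partly cancel.
- Agreement differs between easy and hard cases by g_c points under control and g_d points under the device.

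The easy share is f + 0.5(1 − f) = 0.5 + 0.5f in the device arm and 0.5 − 0.5f in control. Steering raises device agreement by 0.5·f·g_d and lowers control agreement by 0.5·f·g_c, so

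bias = 0.5 × f × (g_d + g_c).

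The planned 90% limits g_d. With half easy cases, the easy and hard percentages sum to 2 × 90 = 180. Easy cannot exceed 100, so hard is at least 80 and g_d is at most 20.

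| f | g_c (points) | Bias with g_d = 20 | Bias with g_d = 0 |
|---|---|---|---|
| 10% | 20 | 0.5 × 0.10 × 40 = 2 | 1 |
| 20% | 30 | 0.5 × 0.20 × 50 = 5 | 3 |
| 30% | 40 | 0.5 × 0.30 × 60 = 9 | 6 |

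With g_d at its cap, the bias is 2/41 = 5% to 9/41 = 22% of the planned contrast.

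**5. If the device had no effect.** The 41-point contrast rests on a simulator trial, so the null case is worth a look. The 90% cap does not apply to it. In 200,000 simulated trials per setting, with 25 per arm and 49% agreement overall, the planned two-sided t-test rejected in 6.5% of trials with no selection gap between the arms and in 13.2% with a 10-point gap. The gap is assumed. The result shows only that a modest one would affect the test.

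**The case against.** The strongest reply is that this is a gap in description and not evidence of an open list. The text does not say that the coordinator keeps the matrix or can see upcoming rows; what is described as sequential is the Subject Number. A reader might infer that the coordinator holds an open list, but the documents do not support that. Concealment may exist in practice.

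A reader might also infer that the arm can govern which woman is approached. The text points the other way. Hospital providers make the first approach, no section gives them the matrix, sessions are arranged jointly with hospital staff, and Recruitment and Informed Consent says that all eligible patients will be offered participation. The coordinator is employed by the host institution and not by the sponsor.

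Finally, f and the two gaps appear nowhere in the documents. Using one gap of 30 or 40 points in both arms would suggest biases of 6 or 12 points (f × g), but those conflict with the planned 90% device agreement.

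These replies hold as limits on the point. They leave a narrower route: the timing of sessions and the completion of consent, both involving the person who allocates. They do not rescue the claim about bias, because none of these features hides the sequence.

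**Conclusion.** The point holds in this form: no concealment is described, the next arm could therefore be known before consent is completed, and both statements that computer generation eliminates assignment bias claim more than generation provides. This is more than a missing detail, because the procedure as written leaves the primary comparison of an open-label, 50-patient trial open to selective entry.

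The size is unknown. Under the stated assumptions it is about 2 to 9 points against the planned 41, with the device-arm gap at its cap of 20 points and all steering in one direction. It would be smaller if device agreement depended less on ease of measurement.

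A reader might go further and infer that selection will occur, or that it could by itself produce the planned contrast. The documents show no steering, and the illustration falls well short of 41 points. The plan should be changed, but the trial is not invalid on this ground.

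**What to change.** 1. State who generates and holds the list: existing personnel with no part in enrollment (for example a statistician at the sponsor or the institution) or an electronic randomization module. State any blocking.
2. Release each arm by sequentially numbered, opaque, sealed envelope or by electronic release, and only after the consent form is signed and the Subject Number and time are logged.
3. Reword the Bias paragraph and the Randomization paragraph under Protection of Human Subjects, so that protection against assignment bias is attributed to random generation together with concealment until enrollment is logged.

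If such a procedure is already in use, only the text needs to change. Otherwise the cost is 50 envelopes or one electronic form, minor set-up work, and a small task for someone outside enrollment, a role the protocol does not yet name. No further patients are needed, and no figure in the sample-size section changes.

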The second provider will enter the hospital room. The second provider will introduce him/herself to the patient and explain that s/he is going to perform a cervical examination. The trial coordinator will record the time of the second exam. The second exam must be completed within 10 minutes of the first exam. The second provider will complete a cervical examination following standard techniques. The provider will write his/her measurement of cervical dilation on a second Data Collection Form, fold the form, and hand it to the trial coordinator. Readings may be integers or fractional answers. The second provider will leave the room.

If the patient is in the Device Group: The first provider will introduce him/herself and inform the patient that s/he is going to conduct a cervical examination and confirm that the patient is ready to proceed. The trial coordinator will record the time of the first exam. The first provider will complete a cervical examination with a DilaCheck® device and sterile gloves using the techniques taught during training.

During or after the examination, before looking at the DilaCheck® device or his/her hand, the provider will verbally report his/her subjective cervical dilation measurement to the trial coordinator. Readings may be integers or fractional answers. The trial coordinator will record this number. The first provider will then look at the DilaCheck® device and read the measurement from the DilaCheck® measuring tape.

The trial coordinator will take a photograph from a secure camera of the DilaCheck® measurement. The trial coordinator may choose to take multiple photographs to ensure a clear image is captured. The coordinator and provider will use a neutral background to ensure no private health information (such as an image of the patient participant or hospital room) is included in the photograph. A white sheet of paper with the subject number will be provided to serve as a blank, secure background for the photograph(s).

The first provider will record two readings of the DilaCheck® measurement. The provider will write his/her measurements on the first Data Collection Form, fold the form, and hand it to the trial coordinator. The first will be his or her reading of the exact DilaCheck® measurement, which may be a fraction (any fraction). The second reading will be his or her reading of the DilaCheck® measurement rounded to the nearest integer; i.e. the second response can only be an integer, not a fraction.

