The first provider will dispose of the gloves and device. The first provider will then leave the hospital room. S/he will not speak to the second provider.

The second provider will enter the hospital room. The second provider will introduce him/herself to the patient and explain that s/he is going to perform a cervical examination. The trial coordinator will record the time of the second exam. The second exam must be completed within 10 minutes of the first exam. The second provider will complete a cervical examination as above using a DilaCheck® device. The second provider and trial coordinator will repeat the same steps as described above for the first provider. The second provider will leave the room.

Patient Survey. The trial coordinator will then ask the patient to answer the questions on the Patient Survey. The survey will elicit relevant biological and demographic variables including age, race, ethnicity, gestational age, weight, and use of epidural anesthesia. It will assess the patient's discomfort with the examinations, confidence in the accuracy of the measurements, and satisfaction with the examinations. Patients will be asked to report any side effects they experienced and to provide any comments they have.

Patient Reimbursement. The trial coordinator will offer the patient a \$25 gift certificate to thank her for participating. The patient will sign a receipt to confirm that she received the gift certificate.

Provider Survey. At the end of the trial, the trial coordinator will ask all participating providers to complete the Provider Survey. The survey will elicit the provider's years of experience, role on Labor and Delivery, opinions about inter-examiner agreement using standard methods and using DilaCheck®, and ease of use and satisfaction with the device. The survey will ask whether providers experienced any adverse events and if their patients experienced any adverse events during the trial. They will have the option to provide comments.

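### Only the device arm's procedure gives the coordinator, and probably the patient, the first examiner's values before the second exam, so masking of the second examiner is weaker in that arm

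*Combined protocol and SAP*

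**What the plan says.** All of this is in the Trial Protocol part of the combined document.

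- **Both arms (Data Collection, before the split by group).** "The second provider will wait outside the room, in a place where s/he cannot hear the interaction in the room". In each arm the first provider then leaves, and "S/he will not speak to the second provider".
- **Control Group.** The first provider writes the reading and folds the form. "The coordinator will take the folded sheet of paper and will not read the value".
- **Device Group, subjective estimate.** Before looking at the device or hand, "the provider will verbally report his/her subjective cervical dilation measurement to the trial coordinator". "The trial coordinator will record this number".
- **Device Group, tape reading.** "The trial coordinator will take a photograph from a secure camera of the DilaCheck® measurement". Then: "The provider will write his/her measurements on the first Data Collection Form, fold the form, and hand it to the trial coordinator". The instruction not to read the form is not repeated here.
- **Device Group, second examination.** The coordinator goes through the same steps with the second provider, and so is in the room.
- **Bias.** Patients and providers cannot be blinded to group. The section names two protections: "keeping the second provider blinded" to the first reading, and computer randomization, which deals with assignment.

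**The concern.** The primary outcome is agreement between two readings on the same woman, so it depends on the second reading being made independently of the first. The control-arm text treats the coordinator as a possible channel and closes it. The device-arm text opens that channel. The coordinator hears and records one value and sees the other, and the patient is in the room while the estimate is spoken. Both are there when the second provider examines.

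If values or hints pass along this route, they do so mainly in the arm expected to show better agreement. Part of any observed difference could then come from the procedure and not from the device. Once the data are collected, such a leak could be neither measured nor removed.

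**Working it through.** **Step 1. Who knows the first examiner's values when the second exam begins?**

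| | Control Group | Device Group |
|---|---|---|
| How the first value is given | Written, folded | Subjective estimate spoken; tape readings written, folded |
| Coordinator knows a value | No, by instruction | Yes: records the estimate, photographs the tape |
| Coordinator barred from reading the form | Yes | Not stated |
| Patient may know a value | Nothing calls for it, nothing forbids it | Probably hears the estimate (inferred from the setting) |
| Second provider out of earshot | Yes | Yes |
| First provider does not speak to second | Yes | Yes |
| Coordinator or patient told not to disclose | Not stated | Not stated |

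The last three rows are the same in both arms. The arms differ in the rows above them.

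**Step 2. Which value bears on the primary outcome?** The Statistical Analysis section compares the two providers' readings, using the fractional and integer DilaCheck readings in the device arm. The spoken number is the subjective estimate and is not the primary reading. The coordinator's view of the tape is the route that concerns the primary reading itself.

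**Step 3. Size if the cue is the tape reading.** The documents give no figure for leakage. Let p be true device-arm agreement and q the share of device pairs in which the second examiner is cued to the first tape reading and then agrees. Of those pairs, a share 1 - p would otherwise have disagreed, so observed agreement rises by q(1 - p). The values of p are the Power Calculation's projections, 90% (device) and 49% (control). The range q = 10-20% is an assumption.

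- p = 0.90: 0.10 × 0.10 = 0.010 and 0.20 × 0.10 = 0.020, so +1 to +2 points.
- p = 0.49: 0.10 × 0.51 = 0.051 and 0.20 × 0.51 = 0.102, so about +5 to +10 points.

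For scale, the planned difference is 90 - 49 = 41 points, and one pair out of 25 is 100/25 = 4 points.

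**Step 4. What that would do to the test if the device had no effect.** Take true agreement of 49% in both arms and 25 pairs per arm. Apply the planned t test to agreement coded 0/1, with exact binomial enumeration. Suppose a share of the device-arm disagreements is turned into agreement.

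| Share converted (assumed) | Device-arm agreement | Chance of a significant result favouring the device |
|---|---|---|
| 0 | 49.0% | 3.2% |
| 10% | 0.49 + 0.10 × 0.51 = 54.1% | 6.9% |
| 20% | 0.49 + 0.20 × 0.51 = 59.2% | 13.0% |

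These figures hold only if every cue conveys the tape reading and is followed.

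**Step 5. Direction if the cue is the spoken estimate.** A second examiner anchored to that estimate moves toward it, and it may differ from the first tape reading. As an illustration only, suppose the estimate matches the first tape reading 46% of the time (borrowing the simulator accuracy of standard methods from the Protocol Summary) and a cued examiner reproduces the estimate. Agreement then changes by q(0.46 - p). At p = 0.90 this is 0.10 × (-0.44) = -4.4 points to 0.20 × (-0.44) = -8.8 points. The sign of this route is therefore not fixed.

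**The case against.** The strongest reply is that the primary device readings are written and folded, that the second provider is out of earshot, and that the two providers do not speak. The spoken number is a secondary measure. Every tape is also photographed and read by an independent, blinded reader, so a second examiner who merely wrote down a cued number would be contradicted by the photograph. At the protocol's own 90% projection, the assumed leak moves agreement by less than one pair in 25.

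Much of this stands. Direct transfer is blocked, and the photograph guards against simple misreporting. But the photograph does not guard against a cue that changes how the examination is done, and the reader's values enter the plan as a correlation with the providers' readings, not as the primary agreement comparison. The out-of-earshot and no-speaking rules do not cover the coordinator or the patient.

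A reader might infer more than the text supports:

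- **That any leak can only raise device-arm agreement.** This is not so for the spoken estimate, as Step 5 shows.
- **That the control arm is leak-proof.** The coordinator is kept from the value there, but nothing stops the first provider from telling the patient.
- **That agreement between the two subjective estimates is at risk as a planned result.** No such analysis is specified. The planned subjective analyses are correlations with the tape.

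**Conclusion.** The point holds as an asymmetry in procedure: masking of the second examiner is weaker in the device arm. It would go too far to say that masking is broken or that a bias has been shown. The remaining route is indirect, through the coordinator or the patient, and that the patient hears the estimate is inferred from her presence.

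A cue about the tape reading would tend to favour the device. A cue about the spoken estimate has no certain direction. Under the assumed 10-20% cueing to the tape reading, the gain is +1 to +2 points at 90% true agreement and about +5 to +10 points at 49%. It matters little if the device performs as projected, and more if it does not. The leak rate is an assumption throughout. The change is worth making because it is nearly free and the problem cannot be repaired afterwards.

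**What to change.** 1. **Both arms.** Add a scripted instruction that the first provider, the coordinator and the patient do not mention or hint at any value until both examinations are complete.
2. **Device arm, subjective estimate.** Capture it silently and out of the patient's sight, while keeping the rule that it comes before the provider looks at the device or hand. For example, the provider points to a number on a card that the coordinator holds away from the examining hand, and the coordinator records it without saying it aloud. Having the provider write on a card would risk a glimpse of the hand or device.
3. **Device arm, form and photograph.** Repeat the control arm's no-read rule for the folded form. Have the coordinator put the photograph and the recorded number out of view before the second provider enters.

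The coordinator will still know both values, having recorded one and photographed the other, so the non-disclosure rule is the main protection. The cost is a card, a short script and a few seconds more handling per device examination. Sample size and analysis do not change.
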